1 SYNOPSIS

| Title: A Randomized, Double-Blind, Placebo-Controlled, Multiple Dose Study to Assess the Safety and Efficacy of Elezanumab when Added to Standard of Care in Progressive Forms of Multiple Sclerosis | | |
|--|---|--|
| Background and Rationale: | Elezanumab is an investigational product under development for the treatment of multiple sclerosis (MS). It is a monoclonal immunoglobulin (Ig) of the human IgG1 isotype that binds specifically to the soluble and the membrane-bound forms of repulsive guidance molecule A (RGMa). Elezanumab is being evaluated to determine if RGMa neutralization leads to neural restoration and functional improvement in MS patients. | |
| Objectives and Endpoints: | To evaluate the safety and efficacy of elezanumab in subjects with progressive forms of multiple sclerosis (PMS). Primary endpoint: Mean Overall Response Score (ORS) at Week 52. ORS is a composite score derived from 4 components: Expanded Disability Status Scale (EDSS) Timed 25-Foot Walk (T25FW) 9-Hole Peg Test in the dominant hand (9HPT-D) 9HPT in the non-dominant hand (9HPT-ND) | |
| Investigators: | Multicenter | |
| Study Sites: | Approximately 30 sites in the United States and Canada | |
| Study Population and Number of Subjects to be Enrolled: | Approximately 90 subjects with PMS (approximately 60 primary- progressive MS [PPMS] subjects and approximately 30 secondary- progressive MS [SPMS] subjects) | |
| Investigational Plan: | This is a 52-week, Phase 2a, proof-of concept, randomized, double- blinded, parallel-group, placebo-controlled multicenter study to evaluate the safety and efficacy of 2 doses of elezanumab in adult subjects with PMS. | |
| Key Eligibility Criteria: | Adult male or female, between 18 and 65 years of age, inclusive, with a diagnosis of PPMS or non-relapsing SPMS according to the 2017 revised McDonald criteria, and evidence of physical disability (EDSS score of 2 to 6.5 or T25FW \geq 8 sec or 9HPT \geq 33 sec) and no relapses for at least 24 months. | |
| Study Drug and Duration of Treatment: | Eligible subjects will be randomized at the Week 0 - Baseline Visit to receive either elezanumab or as an intravenous (IV) infusion or placebo in a 1:1:1 ratio. Blinded doses will be administered intravenously every 4 weeks for 48 weeks. Subjects will remain on their current immunomodulatory treatment regimen. | |
| Date of Protocol Synopsis: | 19 March 2021 | |

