7 STATISTICAL METHODS & DETERMINATION OF SAMPLE SIZE

7.1 Statistical and Analytical Plans

Complete and specific details of the statistical analysis will be described and fully documented in the statistical analysis plan (SAP). The SAP will be finalized before the interim database lock. The statistical analyses will be performed using SAS (SAS Institute Inc., Cary, North Carolina, USA).

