7.3 Statistical Analyses for Efficacy

The ORS scores will be summarized descriptively (including n, mean, standard deviation, minimum, median, and maximum) along with the 95% confidence interval at each visit. The frequency and percentage of ORS for –4 to +4 will also be provided by treatment group at each visit. The ORS for each treatment group at scheduled visits and overall will also be estimated using a mixed-effect model for repeated measures (MMRM) including treatment group, visit, treatment-by-visit interaction, and stratification factors as fixed effects, with the baseline values for the ORS components as covariates.

For other continuous efficacy endpoints, the mean, standard deviation, median, minimum and maximum will be reported for each treatment group. The treatment comparison will be conducted using MMRM model including treatment group, visit, treatment-by-visit interaction, and stratification factors as fixed effects and the baseline value associated with the endpoint as a covariate.

For binary efficacy endpoints, the frequency and percentage will be provided by treatment group. The treatment comparison will be conducted using a logistic regression model adjusted for the stratification factors and baseline score associated with the endpoint.

All efficacy endpoints will be analyzed on mITT population. The RF and MMIA Sets will be used for the primary and other efficacy analyses as specified in the SAP.

Sample Size Estimation

Approximately 90 subjects will be equally randomized 1:1:1 to each treatment group (30 subjects in each treatment group, with a target of 20 PPMS subjects and approximately 10 SPMS subjects per treatment group). There is limited prior data to estimate the magnitude of effect and variance for a neurorestorative therapy. The sample size was therefore selected based on operational feasibility, variance seen in prior MS trials, and the likelihood of predicting success in subsequent phases of development.

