4.3 Endpoint

4.3.1 Primary Efficacy Endpoint

The primary efficacy endpoint is the Overall Response Score (ORS) at Week 52.

ORS is a composite score derived from 4 components:

- Expanded Disability Status Scale (EDSS)
- Timed 25-Foot Walk (T25FW)
- 9-Hole Peg Test in the dominant hand (9HPT-D)
- 9HPT in the non-dominant hand (9HPT-ND)

The EDSS + is a composite derived from the EDSS, T25FW, 9HPT-D and 9HPT-ND where responder status is defined as a clinical meaningful improvement on one or more of these endpoints. Hereafter, the EDSS, T25FW, 9HPT-D and 9HPT-ND will also be referred to as "components of the EDSS +" or "components of the ORS."

The ORS is scored with a range from -4 to +4 at each assessment for all post-baseline visits. Scores for each component are assessed relative to their baseline value: -1 if there is clinically significant worsening, 0 if the change does not meet the clinically significant threshold criteria, or +1 if there is clinically significant improvement. The scores for all components are summed at each assessment. If any of the 4 components of the ORS are missing within a visit window, then the ORS will be considered missing for that visit.

The clinically significant change thresholds for EDSS, T25FW and 9HPT are provided in the following table.

	Score of ORS Components at Post-Baseline Visits			
ORS Components	-1 (Clinically Significant Worsening)	0 (No Clinically Significant Change)	l (Clinically Significant Improvement)	
EDSS change from baseline	\geq 1 if baseline EDSS \leq 5.5; \geq 0.5 if baseline EDSS \geq 6.0	-0.5, 0 or 0.5 if baseline EDSS $\leq 5.5;$ 0 if baseline EDSS ≥ 6.0	≤ -1 if baseline EDSS ≤ 5.5 ; ≤ -0.5 if baseline EDSS ≥ 6.0	
T25FW change from baseline	≥20%	> -20% and < 20%	\leq -20%	
9HPT-D change from baseline	\geq 20%	> -20% and < 20%	\leq -20%	
9HPT-ND change from baseline	≥20%	> -20% and < 20%	\leq -20%	

4.3.2 **Secondary Efficacy Endpoints**

The secondary efficacy endpoints include:

- Disability improvement responder status (Yes or No) on the EDSS+
- ORS at Weeks 12, 24, and 36

Exploratory Efficacy Endpoints 4.3.3

The exploratory efficacy endpoints include:

- Disability improvement response rate on the EDSS, T25FW, 9HPT-D, and 9HPT-ND at Weeks 12, 24, 36, and 52, and the EDSS + at Weeks 12, 24, and 36.
- Change from Baseline on the T25FW, 9HPT-D, 9HPT-ND at Weeks 12, 24, 36, and 52

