- Disability progression response rate on the Expanded Disability Status Scale Plus (EDSS +) (T25FW, 9-Hole Peg test [9HPT, either hand], EDSS) and for each EDSS + component
- 12- and 24-week confirmed disability improvement response rate on the EDSS + and for each EDSS + component
- Change from Baseline on the Multiple Sclerosis Impact Scale (MSIS-29) total score at Weeks 12, 24, 36, and 52
- Change from Baseline on the Modified Fatigue Impact Scale (MFIS) total score at Weeks 12, 24, 36, and 52
- Change from Baseline on cognition battery at Weeks 12, 24, 36, and 52:
 - Total score of the Symbol Digit Modalities Test (SDMT) Oral Version
 - Total score and T-score of the Brief Assessment of Cognition Verbal Memory - Immediate Recall – BAC App Version
 - Total score and T-score of the Brief Assessment of Cognition Tower of London – BAC App Version
- Change from Baseline on the Low Contrast Visual Acuity (LCVA) assessments at Weeks 12, 24, 36, and 52
- Change from Baseline in select plasma biomarkers for monitoring target binding, neuroprotection and/or neurorestoration at Weeks 12, 24, 36, and 52
- Change from Baseline on the MS Individualized Outcome Assessment (MSIOA) overall symptom score and most bothersome symptom score scale at Weeks 24, and 52
- Change from Week 0 in average daily step count and other activity measures (as described in Section 9.4.3) via home actigraphy with wearable biosensor initiated at Weeks 24, 36, and 52
- Summary of variables from brain MRI at Baseline, Weeks 24 and 52
 - Presence of active lesions T1 Gadolinium (GAD)-enhancing lesions
 - Presence of active new and enlarging T2 hyperintense lesions
 - Cumulative number of total T1 GAD-enhancing lesions
 - Cumulative number of total T2 hyperintense lesions
 - Cumulative number of post-baseline T1 GAD-enhancing lesions

- Cumulative number of post-baseline new and enlarging T2 lesions
- Number of T1 GAD-enhancing lesions at each visit
- Change from Baseline in total volumes of (T1 GAD-enhancing lesions)
- Change from Baseline in total volume of T2 hyperintense lesions
- Change from Baseline in whole brain, gray matter (GM), thalamus, white matter (WM) and normal appearing white matter (NAWM) volumes
- Change from Baseline in regional magnetization transfer ratio (MTR) parameters for whole brain, and NAWM, and MTR for T2 lesions
- Change from baseline in lesion MTR for T1 (GAD)-enhancing lesions and delta MTR

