Improvement responder status on the EDSS + and each of its components will be analyzed by time point based on the criteria in Section 4.3.1. No confirmation will be required, i.e., improvement at the analysis time point only is required to be considered a responder.

The analysis will be presented at each time point with the number and percentage of responders, and the 95% confidence interval for the proportion of subjects based on Wald confidence limits, and the odds ratio and corresponding 95% confidence interval based on the logistic regression model including baseline as a covariate and treatment as a main effect. The model for the EDSS + will include the baseline EDSS, baseline T25FW, baseline 9HPT-D, baseline 9HPT-ND as covariates and treatment as a main effect. This will be presented based on the mITT, RF and MMIA analysis sets using non-responder

imputation. The logistic regression analysis will be repeated for the mITT analysis set based on the same multiple imputation as detailed in Section 9.3.1.

A summary of the improvement responder status on the EDSS + and each of its components will be presented for the mITT analysis set as observed.

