9.4 Other Efficacy Analyses

Change from baseline treatment comparison at each visit will be conducted using an MMRM model including treatment group, visit, treatment-by-visit interaction, and stratification factors as fixed effects, the baseline values associated with the endpoint as covariates. The REPEATED statement will be used for visit with blocks in the covariance matrix identified by subject nested within treatment group. The unstructured covariance structure will be used to estimate the within subject variance-covariance. If the model fails to converge, the first order autoregressive (AR[1]) covariance structure will be substituted. If the model still fails to converge, the compound symmetry (CS) covariance structure will be substituted. Denominator degrees of freedom will be computed using the Kenward-Roger method.

For binary efficacy endpoints, the frequency and percentage will be provided by treatment group unless otherwise noted.

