9.4.1 Confirmed Improvement on the EDSS + and its components

Confirmed 12-week disability improvement on the EDSS + or components of the EDSS + indicates a subject has clinically significant improvement at a visit as well as the next visit for one or more EDSS + components, or if the next visit is missing, the subsequent visit. Confirmation may include assessments collected in the post-treatment follow-up period. The improvement confirmation must be in the same component of the EDSS +. If a subject has improvement in more than one component of the EDSS +, the subject must have confirmation in at least one of the same components to be considered as having confirmed disability improvement. For example, if a subject has clinically significant improvement in the T25FW at Week 12, the subject must have clinically significant improvement in the same component of the EDSS + at Week 24 (or if Week 24 is missing, Week 36) to be considered to have confirmed improvement.

Confirmed 24-week improvement on the EDSS + or components of the EDSS + indicates a subject has clinically significant improvement at 3 consecutive visits, or if one of the two subsequent visits are missing, subject demonstrates clinically significant

improvement at two of the subsequent three visits. Improvement status after confirmed improvement is not considered, i.e., if a subject has disability improvement in one component of the EDSS + at Week 12 and Week 24, then this subject is considered to have 12-week confirmed disability improvement regardless of a Week 36 status of clinically significant worsening, no clinically significant change, or clinically significant improvement.

The 12-week and 24-week confirmed disability improvement response rate will be summarized for the study for the EDSS +, as well as each of the individual components for the mITT, RF, and MMIA analysis sets based on a non-responder imputation. The frequency and percentage will be provided by treatment group. The treatment comparison will be conducted using the logistic regression model adjusted for the stratification factors and baseline scores associated with the endpoint. The proportion of responders, difference in responder rate, and 95% confidence interval for the responder rate based on Wald confidence limits will be presented based on the univariate summary. The odds ratio, and 95% confidence interval will be derived from the logistic regression model.

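### SAP 9.3 models EDSS+ improvement response without the stratification factors that Protocol 7.3 calls for, and neither document explains the difference

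*SAP*

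**What the plan says.** - **Protocol 7.3**, for binary efficacy endpoints, prescribes a "logistic regression model adjusted for the stratification factors and baseline score associated with the endpoint".
- **SAP 4.3.2** lists as a secondary endpoint "Disability improvement responder status (Yes or No) on the EDSS"+. Protocol 3.3 places it at Week 52.
- **SAP 9.3** gives the logistic model twice: once in general form (baseline and treatment) and once for the composite: "The model for the EDSS + will include the baseline EDSS, baseline T25FW, baseline 9HPT-D, baseline 9HPT-ND as covariates and treatment" as a main effect. No stratification factor is in either.
- **SAP 9.4.2** uses the general form, again without the factors, for exploratory EDSS+ progression.
- **SAP 9.4.1** covers an exploratory endpoint, "12- and 24-week confirmed disability improvement response rate on the EDSS + and for each EDSS + component". There the model is a "logistic regression model adjusted for the stratification factors and baseline scores associated with the endpoint".
- **SAP 9.2** includes diagnosis (PPMS or nrSPMS) and background immunotherapy in the primary MMRM.
- **SAP 9.3.1** puts both factors in the imputation model. The ANCOVA it then applies to the imputed ORS lists only the baseline component values.
- **SAP 4.2.2** takes both factors, for analysis, from the eCRF.

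**The concern.** The two documents lead to two different odds ratios for one secondary endpoint. A reader holding the protocol would expect the one adjusted for the factors used in randomisation and would receive the other without being told. Leaving a prognostic covariate out of a logistic model moves the treatment odds ratio towards 1 and costs some power. The SAP's own usage is uneven, since closely related endpoints are treated differently within a few pages and no reason is given.

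**Working it through.** **1. The plan's own figure.** SAP 4.4 states about 80% power for an effect size of 0.59, one-sided 0.10, with 10% dropout. With 30 × 0.9 = 27 evaluable per group, power = Φ(0.59 × √(27/2) − 1.282) = Φ(2.168 − 1.282) = 0.812 (0.808 by noncentral t). It reproduces. It concerns a t-test, and nothing below changes it.

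**2. The models side by side.**

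| Analysis | Status | Baseline scores | Stratification factors |
|---|---|---|---|
| Protocol 7.3, binary endpoints | general rule | yes | yes |
| SAP 9.3, EDSS+ improvement | secondary | four components | no |
| SAP 9.4.2, EDSS+ progression | exploratory | yes | no |
| SAP 9.4.1, confirmed improvement | exploratory | yes | yes |
| SAP 9.2, ORS by MMRM | primary | four components | yes |
| SAP 9.3.1, ORS by ANCOVA after MI | sensitivity | four components | no |

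**3. Does another section restore the factors?** SAP 4.2.2 names only their data source. SAP 9.4 puts them in the general MMRM, but for binary outcomes says: "For binary efficacy endpoints, the frequency and percentage will be provided by treatment group unless otherwise noted". SAP 11.1 mentions no change of covariates, and neither does Protocol Appendix E.

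**4. Direction of the effect, large sample.** The documents give no response rates or factor effects, so these inputs are assumptions. Take logit(p) = −1 + ln(3)·T + b(A − 1/3) + b(C − 1/2), where T is treatment and A and C are binary factors with prevalence 1/3 and 1/2.

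| OR of each factor, exp(b) | Treatment OR, factors omitted | Factors included | Ratio |
|---|---|---|---|
| 1.65 | 2.92 | 3.00 | 0.97 |
| 2.72 | 2.69 | 3.00 | 0.90 |
| 4.48 | 2.42 | 2.98 | 0.81 |

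**5. Size in a trial like this one.** The check used 10,000 simulated trials per scenario.
- Taken from the documents: N = 90, 60 PPMS and 30 SPMS, 1:1:1 allocation within the four strata.
- Assumed: blocks of 3, 50% on immunotherapy, placebo response 15% or 25%, true conditional treatment OR 2.5 in both active arms, four baseline scores correlated 0.4 with log OR 0.2 per SD each.
- Test: Wald, one dose against placebo, one-sided 0.10.

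| OR of each factor | Median OR, SAP model | Median OR, protocol model | Power lost by SAP model, points | Ratio of the two ORs within a trial: median; 90th percentile |
|---|---|---|---|---|
| 1 | 2.7 | 2.8 | 0.4–0.6 | 1.02–1.03; 1.11–1.14 |
| 2 | 2.6 | 2.8 | 1.8–2.0 | 1.06–1.07; 1.26–1.30 |
| 3 | 2.4–2.5 | 2.8–2.9 | 2.9–3.6 | 1.13; 1.47–1.54 |

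The Monte Carlo standard error of the power differences is 0.11–0.22 points. The two models reach different verdicts in 1–2%, 3–4% and 5% of trials respectively. Null rejection is 9.1–10.7% for the SAP model and 10.2–11.4% for the protocol model. A separate re-run (1,500 trials per scenario, 15% placebo response) gave a power gain of about 0 to 4 points, with null rejection of 10–11% and 10–12%.

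**6. Sparsity.** The SAP model has 2 treatment terms + 4 scores = 6 terms, and the protocol model has 6 + 2 = 8. With 0.15 × 90 = 13.5 responders, that is 13.5/6 = 2.25 against 13.5/8 = 1.69 per term. With 0.25 × 90 = 22.5, it is 3.75 against 2.81.

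**The case against.** Several parts of the opposing case stand.

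- **The SAP may be the operative text.** Protocol 7.1 says "Complete and specific details of the statistical analysis will be described and fully documented in the statistical analysis plan", and SAP 9.3 writes the model out. This is a fair reading. But adding detail is different from leaving out covariates that the protocol names, and delegation does not remove the need to say so.
- **A reader might infer that the factors were deleted between SAP versions.** The documents do not show this. SAP version 1 is not available, and SAP 11.1 lists by-visit EDSS+ improvement and disability progression as added analyses, so its silence on covariates proves nothing about a removal.
- **A reader might infer that the later protocol reaffirms the adjusted model**, since it carries "Date of Protocol Synopsis: | 19 March 2021" and SAP 2.0 is dated 06 January 2021. Appendix E says that version was made to remove the on-site Week 64 and 76 assessments, plus administrative revisions. Text carried over in Section 7.3 is weak evidence of intent.
- **A reader might extend the point to the SDMT responder model in SAP 9.4.6**, which has the same form. That responder is not a listed endpoint in either document, so Protocol 7.3 does not clearly govern it.
- **A shorter model is defensible when responders are few.** True, but the SAP does not give that reason. It also keeps the factors for confirmed improvement, which needs the threshold met again in the same component. Sparsity is therefore an unlikely explanation, though not impossible, because confirmation can occur at any visit.
- **The adjusted model can be unstable if one immunotherapy stratum is small.** SAP 5.2 itself allows for a stratum below 20%. With 85–90% on immunotherapy, under the null, some coefficient was unstable in 15–46% of adjusted fits at 15% response (SAP model about 2–2.6%) and in 3–25% at 25% response (SAP model under 0.1%). This stands, but the instability lies in the factor coefficient. The treatment odds ratio was unstable equally often under both models, in 1.2% of trials or fewer.

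**Conclusion.** The point holds as an unexplained departure of SAP 9.3, and of SAP 9.4.2, from the model in Protocol 7.3. Its practical weight is low: this is a secondary endpoint in a proof-of-concept study with no multiplicity control, and Protocol Appendix E reports no efficacy on any endpoint.

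The primary MMRM is unaffected. The MI sensitivity ANCOVA for ORS also lists no stratification factors, but the protocol sets no model for it, so that is a gap to note and not a contradiction.

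The size rests on assumed factor odds ratios of 1 to 3 and on borrowing the one-sided 0.10 level from SAP 4.4, since SAP 9.3 reports an odds ratio with a 95% interval and names no test. On that footing the protocol model gains about 0 to 4 points of power, part of which reflects its slightly higher null rejection. If the factors carry no information beyond the baseline scores, the difference is close to nothing.

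Two stronger conclusions should be avoided. The SAP model adds no false-positive risk. Nor is its odds ratio shown to be less accurate: small-sample bias lifts the protocol model's median to 2.8–2.9 against a true 2.5, while the SAP model's is 2.4–2.7.

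**What to change.** For EDSS+ improvement response at Week 52, report the logistic model of Protocol 7.3: treatment, the four baseline component scores, diagnosis (PPMS or nrSPMS) and background immunotherapy (Yes or No), with both factors as recorded on the eCRF under SAP 4.2.2. Set the SAP 9.3 model beside it and state in the study report that the two documents differ. The study report is the place for this because the efficacy analysis has already been run. Treat progression under SAP 9.4.2 the same way.

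The cost is one extra model run per endpoint and no new data. The downsides are two more terms with few responders, slightly higher null rejection, and a factor coefficient that may not be estimable if one immunotherapy stratum is small. If that happens, say so; the treatment odds ratio can still be given.

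Single-component responses can be left descriptive where they are rare. With about 8.5 responders there was no stable fit in 14–15% of trials without the factors and 18–22% with them. With about 4 responders the shares were 55–56% and 63–69%. Neither model can be relied on there.
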